#### **Handling of missing data:**

Missing primary efficacy data in mITT will be imputed as follows:

#### Full Mayo Score at Visit 7:

- Subjects with missing Mayo Score at visit 7 will be imputed with the post-screening Full Mayo Score (obtained from early discontinuation or unscheduled visit) according to the date which is most close to visit 7's date of that subject. In other words, visit 7 score will be imputed by last observation carried forward (LOCF) or last observation carried backward (LOCB) depending on the date of the score. Note: Imputation will be done only if the score date is no more than ± 4 weeks from Visit 7 date.
- In the case there is non-trivial amount of missing data sensitivity analyses will be explored.

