4.5 REMOVAL, REPLACEMENT, OR EARLY DISCONTINUATION OF SUBJECTS FROM THERAPY OR ASSESSMENT

Subjects are free to discontinue their participation in the study at any time and without prejudice to further treatment. The Investigator must withdraw any subject from the study if that subject requests to be withdrawn, or if it is determined that continuing in the study would result in a significant safety risk to the subject. Withdrawn subjects will not be replaced.

The subject's participation in this study may be discontinued due to the following reasons:

- Subject withdraws consent.
- Intolerable adverse event (any subject experiencing a grade 3 or 4 infusion reaction will be withdrawn from the study).
- Subject's need for medication prohibited by the protocol.

- The Investigator decides that continuing in the study would not be in the subject's best interest.
- The subject is noncompliant with the protocol.
- The subject becomes pregnant.
- Upon the decision of relevant Regulatory Authorities and/or the Institutional Review Board/Independent Ethics Committee (IRB/IEC).

Subjects who progress and/or relapse will be withdrawn from the study at the Investigator's discretion and will be able to receive local standard-of-care.

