5.4 EARLY DISCONTINUATION STUDY VISIT

An early discontinuation study visit will be performed for subjects who withdraw from the study for the reasons specified in Section 4.5.

All reasons for treatment discontinuation will be documented in the source documents as well as the CRF. Only one reason (the most severe) for early discontinuation should be recorded in the CRF. If one of the reasons for discontinuation is an AE – this should be chosen as the reason. Every effort should be made to follow-up these subjects for resolution of AE.

At this visit, flexible sigmoidoscopy with biopsies will be done in addition to the activities relating to the study period at which time the subject discontinuation visit will be performed. That is, if the subject discontinues during the Treatment period, the visit activities will be similar to those described in Section 5.2; likewise, if the subject discontinues during the Follow-up Period, the visit activities will be similar to those described in Section 5.3. Activities may include (but not limited to): AEs, concomitant medications, laboratory tests, vital signs, and physical examination. Appropriate procedures and evaluations will be completed as deemed necessary by the Investigator.

This visit may be performed on the same day as an originally scheduled visit or could be conducted separately. Data collection at these visits should primarily be guided according to principles to protect subject safety and well-being.

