## 7.2 Primary Efficacy Endpoints

Clinical response at Day 56 (Visit 7), defined as:

"Success" ('1')	A decrease from the pre-treatment screening total
	Mayo score of at least 3 points and at least 30%
	AND
	Either a decrease from the pre-treatment screening sub-score for rectal bleeding of at least 1 point, or
	Rectal Bleeding Sub-score of 0 or 1.
"Failure" ('0')	Otherwise

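### An early discontinuation or unscheduled Mayo score is carried to Visit 7 by date alone, so a subject withdrawn for an adverse event, relapse or prohibited UC medication can count as a Day 56 responder

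*SAP*

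**What the plan says.** **The carry rule.** SAP 6.2.1 fills a missing Visit 7 full Mayo score from an early discontinuation or unscheduled visit. The score is picked "according to the date which is most close to visit 7's date of that subject", and the direction is "last observation carried forward (LOCF) or last observation carried backward (LOCB) depending on the date of the score". The only limit is this: "Imputation will be done only if the score date is no more than ± 4 weeks from Visit 7 date". The UCEIS rule in the same section is identical. Sensitivity analyses are left to be explored if much is missing, and none is named.

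**The endpoint.** SAP 7.2 derives response from the total Mayo and rectal bleeding scores alone; everything else is Failure. Remission and mucosal healing in SAP 7.3 are likewise functions of the scores.

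**The population.** The primary analysis is on mITT (SAP 9.4.1). Once a subject has been dosed and has the required full Mayo scores, only a major entry violation excludes them.

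**Withdrawal.** Protocol 4.5 lists intolerable adverse events and need for prohibited medication among the reasons for discontinuation, and makes withdrawal mandatory after a grade 3 or 4 infusion reaction. It adds: "Subjects who progress and/or relapse will be withdrawn from the study at the Investigator's discretion and will be able to receive local standard-of-care". Protocol 4.5.1 asks for an Early Discontinuation Visit whatever the cause, and Appendix A marks full Mayo, sigmoidoscopy and UCEIS at it. On timing, Protocol 5.4 says only: "This visit may be performed on the same day as an originally scheduled visit or could be conducted separately".

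**The concern.** The primary endpoint is meant to describe response to study treatment at Day 56. Under the carry rule, a subject whose treatment failed, or who could not go on with the study, enters the numerator whenever the last available score happens to be good enough. If that score was taken after other UC therapy began, the improvement may belong to that therapy.

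With at most 42 subjects randomized 2:1, one or two subjects of this kind visibly shift a response rate. The plan does not say that this way of counting them is intended. The same carry feeds remission and mucosal healing, and the UCEIS rule repeats it.

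**Working it through.** The plan gives no figure for this point, so there is nothing to reproduce. The check has five steps.

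**1. Which scores can be carried.** Inputs: Visit 7 at Day 56 with a ±3 day window (Protocol Appendix A), and the 4-week limit, 28 days (SAP 6.2.1).

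| Reference day | Earliest (−28) | Latest (+28) |
|---|---|---|
| Day 53 | Day 25 | Day 81 |
| Day 56 (nominal) | Day 28 | Day 84 |
| Day 59 | Day 31 | Day 87 |

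A withdrawn subject may have no Visit 7 date. The SAP does not say what replaces it, so nominal Day 56 is my assumption. Visit 8 (Day 90) supplies nothing: it lies outside the window and has only a partial Mayo.

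**2. Can a withdrawn subject meet the definition?** The required fall is the larger of 3 points and 30% of the screening score, rounded up to a whole point.

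| Screening Mayo | 6 | 7 | 8 | 9 | 10 | 11 | 12 |
|---|---|---|---|---|---|---|---|
| Fall needed | 3 | 3 | 3 | 3 | 3 | 4 | 4 |
| Highest qualifying score | 3 | 4 | 5 | 6 | 7 | 7 | 8 |

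From a screening score of 9 or more, a qualifying score can still lie in the 6–12 entry range. The bleeding criterion is met by a sub-score of 1, even if it was 1 at screening. Example, in the order stool, bleeding, endoscopy, PGA: screening 3+1+3+3 = 10, carried 2+1+2+2 = 7. The fall is 3 points, or 30%. This is a response, although every Mayo entry criterion is still met.

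**3. Does anything block it?** Two traces under the present text:
- Withdrawn for an adverse event, with the discontinuation visit on Day 40: 56 − 40 = 16 days, inside the limit. The score is carried.
- Withdrawn for relapse on Day 40, other UC therapy started, and a single discontinuation visit on Day 54: 56 − 54 = 2 days. The score is carried, although taken on other therapy.

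No section of either document sets such a subject to Failure. Protocol 8.3.1.2 has the same gap, without the time limit.

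**4. Weight of one subject.** Assuming 42 enrolled, all in mITT, 2:1 gives 28 and 14. Then 1/28 = 3.6 points (active) and 1/14 = 7.1 points (placebo).

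**5. Range.** The overstatement in an arm is (share leaving within the window) × (share of those scored responders). If nobody leaves this way, it is 0. With an assumed 5% leaving and 25% of them scored responders, it is 0.05 × 0.25 = 1.25 points. At the assumed extreme of 20% and 100%, it is 20 points.

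Illustration with assumed counts, exact 90% intervals and two-sided Fisher tests:

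| Case | Active | Placebo | Difference | Fisher p |
|---|---|---|---|---|
| All carried scores kept | 14/28 = 50.0% (33.3–66.7) | 4/14 = 28.6% (10.4–54.0) | 21.4 | 0.321 |
| Two active responders recoded | 12/28 = 42.9% (26.9–60.0) | 4/14 = 28.6% | 14.3 | 0.505 |
| One placebo responder recoded | 14/28 = 50.0% | 3/14 = 21.4% (6.1–46.6) | 28.6 | 0.102 |

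The difference can move either way, depending on the arm in which the carried responders sit.

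**The case against.** **Exploratory trial, and already partly mitigated.** The analysis is descriptive, and the SAP has narrowed the protocol's unlimited carry to four weeks. Dropouts are listed with reason, treatment and time (SAP 9.1), so a reader could recode by hand. The per-protocol set uses observed Visit 7 scores only. This lowers the stakes, but the headline estimate is still the mITT rate, and the per-protocol set omits these subjects instead of counting them as failures.

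**It is a choice of estimand.** One may choose to use scores regardless of withdrawal. But a treatment-policy approach needs the status at Day 56 whatever happened, and a score carried from up to four weeks away is not that. The SAP states no such strategy.

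**The criteria still have to be met.** This is true. An untreated relapse will often fail them. Credit is more plausible after an adverse-event withdrawal, or once other therapy has started. Also, a score on other therapy is possible because the documents are silent on timing, not because they permit it expressly.

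**Stronger readings that a reader might infer.**
- *A known direction: reaction withdrawals on active, relapses on placebo.* Protocol 1.3.2 mentions three infusion reactions in bertilimumab trials, but neither document gives withdrawals by arm or reason.
- *A grade 3 reaction at the Day 28 infusion scored as response the same day.* This lies exactly on the 28-day edge, needs a nominal Day 56, and needs a same-day endoscopy that Visit 4 does not schedule. Day 28 is also the last planned dose.
- *The rule preferring a Day 54 score on other therapy to a clean Day 40 one.* This needs two endoscopies in one withdrawn subject. The protocol provides a single discontinuation visit, and its unscheduled-visit text does not call for endoscopy. A single late score is the realistic case.

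**Conclusion.** The point holds as a gap in the rule. Followed as written, the SAP can count a subject withdrawn for an adverse event, progression or relapse, or prohibited UC medication as a Day 56 responder in the primary analysis, including on a score taken after other UC therapy began.

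Size: 3.6 points per subject on active or 7.1 on placebo, for zero or more subjects. This assumes 42 enrolled, everyone in mITT and nominal Day 56 as the reference. The total effect and its direction cannot be derived from the documents.

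A reader might conclude that neither response rate can be interpreted. The documents do not support that: in the illustration, one active subject is worth 3.6 points against an exact 90% interval of 33.3–66.7%. The change is worth making because it is cheap, not because the analysis fails without it.

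**What to change.** Amend SAP 6.2.1 and 7.2–7.3 as follows. Where items 1 and 2 both apply, item 2 decides the binary endpoints.

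1. Never carry a Mayo or UCEIS score dated after the start of other UC therapy. Use the last score before that therapy if it lies in the window; otherwise the subject is Failure for the binary endpoints.
2. Count as Failure for response, remission and mucosal healing any subject who leaves before Visit 7 because of an adverse event, progression or relapse, prohibited UC medication, or death. Restricting the medication reason to UC therapy keeps out items such as vaccines, which Protocol 6.9.2 also prohibits.
3. Use the carry rule for other withdrawal reasons, with nominal Day 56 as the reference date when there is no Visit 7.
4. Keep the present date-only rule as a named sensitivity analysis.

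This is an analysis change only. It needs SAP wording and a flag built from withdrawal reason and concomitant medication dates, both already collected. The CRF holds one reason, with adverse events taking priority (Protocol 5.4), so mixed reasons involving an adverse event become Failure. Response rates may be slightly lower, and some withdrawals for adverse events unrelated to UC will count as Failure; item 4 shows how much this matters. The change does not cover subjects who start other UC therapy but still attend Visit 7; the SAP should state separately how they are scored.

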#### UCEIS (a secondary endpoint that will be analyzed in mITT as well)

- Subjects with missing UCEIS Score at visit 7 will be imputed with the post-screening UCEIS Score (obtained from early discontinuation or unscheduled visit) according to the date which is most close to visit 7's date of that subject. In other words, visit 7 score will be imputed by last observation carried forward (LOCF) or last observation carried backward (LOCB) depending on the date of the score. Note: Imputation will be done only if the score date is no more than ± 4 weeks from Visit 7 date.
- In the case there is non-trivial amount of missing data sensitivity analyses will be explored.

#### 6.2.2 Per Protocol Population (PP)

The per protocol (PP) analysis set will be a subset of mITT subjects who had no major protocol violations likely to affect outcome as determined by blind review and who received at least 2 of 3 study treatments (placebo or bertilimumab) (i.e. "Date of Drug Administration" is not missing) and who had a full Mayo score at screening and at visit 7. A list of major protocol deviations likely to affect outcome will be provided by the Sponsor prior to database lock.

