8.3.1.3 Per Protocol Analysis Set

The per protocol (PP) analysis set will be a subset of mITT subjects who had no major protocol violations likely to affect outcome as determined by blind review and who received at least 2 of 3 study treatments (placebo or bertilimumab) and who had a full Mayo score at screening and at visit 7. Only observed data will be used in PP; primary data will not be imputed.

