8.3.4 Efficacy Endpoints Analysis

Analysis of all efficacy endpoints will be performed on the mITT set. The PP set will be used as supplementary analyses to test the robustness of the results. If deemed appropriate, supportive analyses using multiple imputations for missing data will be performed on the primary and secondary endpoints. Additional exploratory data-driven analyses could be performed with the caveat that any statistical inference will not have any confirmatory value. Because this is an exploratory study, alpha will be set at 0.1 for comparisons between groups.

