#### **Handling of missing data:**

Missing data will not be imputed, i.e. only observed data will be used.

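### The per-protocol set requires an observed Visit 7 Mayo score, so adherent subjects withdrawn earlier for relapse or a severe infusion reaction drop out of it, and comparing it with mITT does not isolate adherence

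*SAP*

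**What the plan says.** **The PP set.** SAP 6.2.2 takes PP as a subset of mITT: subjects with no major violation likely to affect outcome, "who received at least 2 of 3 study treatments" and "who had a full Mayo score at screening and at visit 7". Protocol 8.3.1.3 has the same conditions. On missing data the SAP says "Missing data will not be imputed, i.e. only observed data will be used" and the protocol says "Only observed data will be used in PP; primary data will not be imputed".

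**Withdrawal.** Protocol 4.5 states "Subjects who progress and/or relapse will be withdrawn from the study at the Investigator's discretion", with no time limit. It also lists "Subject's need for medication prohibited by the protocol" as a reason for discontinuation, and withdraws any subject with a grade 3 or 4 infusion reaction. It adds "Withdrawn subjects will not be replaced".

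**What is collected at withdrawal.** Protocol 5.4 requires sigmoidoscopy at the early discontinuation visit, and the schedules (protocol Appendix A, SAP Table 1) mark a full Mayo there. SAP 6.2.1 lets that score stand in for a missing Visit 7 score in mITT if it lies within 4 weeks of Visit 7. PP has no such provision.

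**Role of PP.** Protocol 8.3.4 says "The PP set will be used as supplementary analyses to test the robustness of the results". SAP 9.4.2 repeats the primary response analysis in PP.

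**The concern.** A per-protocol set is meant to differ from the main set by adherence. Here it also differs by whether the subject was still in the study at Day 56. Relapse is the outcome under study, and a severe infusion reaction is a consequence of treatment. Neither is a protocol violation by the subject, yet either can remove someone who meets every other PP condition.

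At stake is how the comparison of mITT with PP is read. A gap between them could come from non-adherence, from failures having been dropped, or from both. Agreement is no firmer evidence, because offsetting losses in the two arms can produce it. PP is also the only robustness check in the plan with a defined population and a defined analysis.

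**Working it through.** **Who is lost.** Take a subject who receives infusions on Days 0, 14 and 28, relapses, is withdrawn before Day 56, and has a full Mayo at the early discontinuation visit.

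- Exposure rule: met.
- Major violation: none.
- mITT: included, and the early score is carried to Visit 7 if it lies within 4 weeks (nominally Day 28 or later, since 56 − 28 = 28).
- PP: excluded, solely by the Visit 7 clause.

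A subject with a grade 3 or 4 infusion reaction at the second or third dose follows the same path through PP.

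**Inputs.** Up to 42 subjects at 2:1 gives 28 active and 14 placebo (42 × 2/3 and 42 × 1/3). The documents give no response, relapse or dropout rate and no power calculation for this sample size, so there is no plan figure to reproduce. The counts below are assumptions.

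**Effect within an arm.** With x responders among n subjects and w failures withdrawn before Visit 7, the rate with everyone kept is x/n and the PP rate is x/(n − w). The PP rate is higher whenever x and w are both above zero. For placebo with x = 4 and n = 14:

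| Failures withdrawn | PP response |
|---|---|
| 0 | 4/14 = 28.6% |
| 2 | 4/12 = 33.3% |
| 4 | 4/10 = 40.0% |
| 6 | 4/8 = 50.0% |

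With 4 withdrawn, the exact 95% interval moves from 8.4–58.1% to 12.2–73.8%.

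**Effect on the difference.** Everyone kept, 14/28 against 4/14 is 50.0% − 28.6% = 21.4 points.

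| Failures withdrawn (active, placebo) | PP active | PP placebo | Difference, points |
|---|---|---|---|
| 0, 4 | 14/28 = 50.0% | 4/10 = 40.0% | 10.0 |
| 4, 4 | 14/24 = 58.3% | 4/10 = 40.0% | 18.3 |
| 6, 3 | 14/22 = 63.6% | 4/11 = 36.4% | 27.3 |
| 6, 0 | 14/22 = 63.6% | 4/14 = 28.6% | 35.1 |

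With no true difference (8/28 against 4/14), PP shows −19.2 points if 2 active and 6 placebo failures go (8/26 against 4/8), and +7.8 if 6 active and none on placebo go (8/22 against 4/14).

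**When every failure is equally likely to be withdrawn.** If p is the true rate and a share s of failures is withdrawn, the expected PP rate is p/(1 − s(1 − p)). For true rates of 50% and 30%:

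- s = 20%: 55.6% − 34.9% = 20.7 points
- s = 40%: 62.5% − 41.7% = 20.8 points
- s = 50%: 66.7% − 46.2% = 20.5 points

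Both rates are clearly inflated, but the difference barely leaves its true 20 points.

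**The case against.** **PP is supplementary and openly a completers set.** This stands, and it limits the weight of the point. The primary analysis is on mITT, where many relapsers withdrawn after about Day 28 already enter through their early-discontinuation score. Non-responders who reach Visit 7 are counted in PP. Withdrawal for relapse is discretionary, and protocol 5.4 allows the discontinuation visit to fall on a scheduled visit. SAP 9.1 lists every exclusion and dropout with its reason, so the losses will be visible. None of this makes PP a measure of adherence.

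**Other checks exist.** Protocol 8.3.4 allows multiple imputation if deemed appropriate, and SAP 6.2.1 says sensitivity analyses will be explored if missing data are non-trivial. Neither is specified. SAP mITT itself requires a post-baseline full Mayo, and PP, as a subset, cannot reveal the losses that this causes.

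**Stronger readings that the documents do not support.** A reader might infer that PP shrinks a real effect whenever placebo subjects relapse more. It need not. At true rates of 50% and 30%, with failures equal to 10% of active and 15% of placebo subjects withdrawn, PP gives 0.50/0.90 − 0.30/0.85 = 55.6% − 35.3% = 20.3 points, slightly above the true 20. Shrinkage needs a larger imbalance: 10% and 25% give 55.6% − 40.0% = 15.6.

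A reader might also cite lost power as evidence of bias. At an assumed 50% against 25%, with 10% and 25% withdrawn as failures, the chance of a Fisher p-value of 0.1 or less falls from 38% to 26%. Losing the same share of subjects with response rates unchanged already gives 31%, so 7 of the 12 points come from smaller numbers. Neither document names that test.

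**Conclusion.** The point holds as a flaw in the definition of a supplementary analysis set. Inclusion in PP depends on events tied to efficacy and tolerability, so a comparison of mITT with PP does not isolate adherence. The response rate in an arm rises with each failure removed, and with about 14 placebo subjects a handful is enough to move it by 10 points or more. The effect on the treatment difference has no fixed direction, and its size cannot be estimated from the documents; every figure above rests on assumed response and withdrawal counts. The mITT result is not changed by this rule.

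**What to change.** In SAP 6.2.2 and protocol 8.3.1.3, replace the Visit 7 condition with: *has an observed full Mayo at Visit 7, or was withdrawn before Visit 7 because of relapse or progression, need for prohibited medication, or an adverse event.* Leave the other PP conditions as they are. For clinical response, remission and mucosal healing:

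- Count withdrawals for relapse or progression, or for need of prohibited medication, as failures.
- For adverse-event withdrawals, use the early-discontinuation full Mayo under the same rule and ±4-week window as mITT, and count as failure if no such score exists. Scoring them all as failures would make a subject with a responding early score a success in mITT and a failure in PP.
- Keep the completers-only table as an extra output, labelled as such and not described as a robustness test.

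The sponsor's list of major deviations should not exclude the same subjects again by another route.

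**Cost.** Revised wording in both documents and one derived flag from data already collected. No rule on treatment or withdrawal changes. PP would no longer be purely observed Visit 7 data and would depend on the recorded reason. Protocol 5.4 allows only one reason in the CRF and gives an adverse event precedence, so some relapses may be recorded as adverse events. Because PP remains a subset of mITT, relapsers with no post-baseline full Mayo stay out under the SAP definition.
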